## Appendix C

**OMNIGene-GUT**  
For microbiome

**COLLECTION DEVICE**

- ← Cap
- ← Tube top
- ← Tube
- Spatula
- ← Stabilizing liquid
- ← Mixing ball

Tube is not designed to stand upright.

**Summary and explanation of the kit:**  
OMNIGene-GUT provides the materials and instructions for collecting and stabilizing microbial DNA from a fecal sample.

**Warnings and precautions:**

- FOR EXTERNAL USE ONLY.
- Do NOT remove the yellow tube top from the tube.
- Do NOT spill the stabilizing liquid in the tube.
- Wash with water if liquid comes in contact with eyes or skin. Do NOT ingest.
- If collecting a liquid fecal sample, see separately provided user instructions.
- Small items may pose a choking hazard.

**Storage:** 15°C to 25°C  
Ship in accordance to applicable regulations covering transport of biological specimens. See MSDS at [www.dnagenotek.com](http://www.dnagenotek.com)

**Label legend:**

-  Collect sample by (Use by)
-  Catalog number
-  Manufacturer
-  Storage instructions
-  Caution: consult instructions for use
-  Lot number

## USER INSTRUCTIONS

**Read all instructions prior to collection**

[figure not shown]
**Procedure:**

- 1** **IMPORTANT PREPARATIONS:**
  - Empty your bladder before beginning the collection.
  - Collect fecal sample free of urine or toilet water.
  - Toilet paper or tissues may be required.
- 2** While holding the yellow tube top, unscrew ONLY the purple cap from the kit and set aside for later use.
 

**IMPORTANT:**  
Do NOT remove the yellow tube top.  
Do NOT spill the stabilizing liquid in the tube.

- 3** Use the spatula to collect a small amount of fecal sample.
 

**IMPORTANT:** Do NOT remove the yellow tube top.

Actual size of fecal sample.
- 4** Transfer the fecal sample into the yellow tube top. Repeat until the sample fills the yellow tube top.
 

[figure not shown]
**IMPORTANT:** Do NOT push sample into the tube.

- 5** Scrape horizontally across the tube top to level the sample and remove any excess. Wipe exterior of tube and top with toilet paper or tissue as needed.
 
- 6** Pick up the purple cap with the solid end facing down and screw onto the yellow tube top until tightly closed.
 

**IMPORTANT:** Do NOT push sample into the tube.

- 7** Shake the sealed tube as hard and fast as possible in a back and forth motion for a minimum of 30 seconds.
 
- 8** The fecal sample will be mixed with the stabilizing liquid in the tube; not all particles will dissolve.
 

**IMPORTANT:** Continue shaking if large particles remain as shown in Figure A.

- 9** Place spatula in original packaging or wrap in toilet paper and discard in garbage.
 

**IMPORTANT:** Send the sample for processing following the delivery instructions supplied separately by the kit provider.

DNA GENOTEK

*Superior samples*  
Proven performance

Made in Canada  
DNA Genotek Inc.  
[name]  
[name]

Toll-free (North America): [name]  
[contact] • [contact]  
[contact]  
[www.dnagenotek.com](http://www.dnagenotek.com)

Australian Sponsor: Emergo Australia, [name]

OMNIGene-GUT (OM-2010) is not available for sale in the United States.

OMNIGene-GUT (OM-200) is for research use only, not for use in diagnostic procedures.

\*OMNIGene is a registered trademark of DNA Genotek Inc.

Some DNA Genotek products may not be available in all geographic regions; contact your sales representative for details.

All DNA Genotek products, white papers and application notes, are available in the support section of our website at [www.dnagenotek.com](http://www.dnagenotek.com).

Patent ([www.dnagenotek.com/legalnotice](http://www.dnagenotek.com/legalnotice))

© 2018 DNA Genotek Inc., a subsidiary of OraSure Technologies, Inc. All rights reserved.

PD-PR-0442|Issue 5/2018-04

Version 01 – 2019-0906

## Appendix D: Neoadjuvant Therapy Surgical Resectability, Ease and Complications Questionnaire

### Questionnaire 1 (Baseline/at time of trial enrollment)

- Surgeon name
- Patient identification
- Date of questionnaire
- Which lymph node basin(s) is involved? (can be more than one)
  - Femoral/Inguinal
  - Iliac/obturator
  - Axilla
  - Cervical
    - Level 1
    - Level 2
    - Level 3
    - Level 4
    - Level 5
  - Popliteal
  - Epitrochlear
  - Other, specify
- Number of involved lymph nodes?
- Largest dimension of largest lymph node?
- Suspected fixation or narrow margin to adjacent anatomic structure? (can be more than one)
  - Skin
  - Muscle/fascia
  - Artery
  - Vein
  - Nerve
- On a scale of 1-10 (1 = most easy, 10 = most difficult) how difficult do you anticipate the surgery will be if done now?
- Any remarks?
- 

### Questionnaire 2 (To be completed at pre-op visit after completion of neoadjuvant therapy)

- Surgeon name
- Patient identificaiton
- Date of questionnaire
- Which lymph node basin(s) is involved? (can be more than one)
  - Femoral/Inguinal

- Iliac/obturator
    - Axilla
    - Cervical
      - Level 1
      - Level 2
      - Level 3
      - Level 4
      - Level 5
    - Popliteal
    - Epitrochlear
    - Other, specify
- Number of involved lymph nodes?
- Largest dimension of largest lymph node?
- Suspected fixation or narrow margin to adjacent anatomic structure? (can be more than one)
  - Skin
  - Muscle/fascia
  - Artery
  - Vein
  - Nerve
- On a scale of 1-10 (1 = most easy, 10 = most difficult) how difficult do you anticipate the surgery will be if done now?
- Do you think the resection is easier or more difficult compared to baseline?
  - No
  - Yes, specify
- Any remarks?

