### 2.3 EXPLORATORY OBJECTIVES

- To assess immunological and molecular features of treatment response and resistance
- To assess circulating markers and correlate them with treatment response and relapse and toxicity
- To assess the impact of neoadjuvant therapy on surgical resectability

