### 4.9.1 Surgical Ease Surveys

Assessment of surgical ease or difficulty after neoadjuvant therapy administration is not currently well understood. In order to obtain data on this important subject, we will be asking collaborating surgical oncologists to complete surveys on the subjective difficulty or ease of surgery compared to comparable surgery in patients who have not undergone neoadjuvant therapy. Surveys will be administered at time of patient trial enrollment, within 1 week of surgical resection and approximately 30 days after surgery is complete. These time-points are selected with the hope of obtaining initial thoughts on surgical difficulty and how this is altered by the neoadjuvant treatment. The 30-day post-operative survey is to capture complications, if any. Sample surveys are located in Appendix D. The surveys will be performed for the purpose of determining if neoadjuvant treatment influences the outcomes of surgery. Data will be recorded utilizing the Prometheus database.

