## Questionnaire 3 ( $\leq$ 30 Days of surgery)

- Surgeon name
- Patient identification
- Date of questionnaire
- Date of surgery
- Which basin(s) did you resect? (can be more than 1)
  - Femoral/Inguinal
  - Iliac/obturator
  - Axilla
  - Cervical
    - Level 1
    - Level 2
    - Level 3
    - Level 4
    - Level 5

- Popliteal
  - Epitrochlear
  - Other, specify
- Date of drain removal
- Did the patient have any complications  $\leq$  30 days postoperatively?
  - No
  - Yes, seroma/lymphocele
    - Please enter Clavien-Dindo Grade .....
  - Yes, surgical site infection
    - Please enter Clavien-Dindo Grade .....
- Was the patient re-operated?
  - No
  - Yes
- Was the patient re-admitted?
  - No
  - Yes
- Did the patient undergo any other interventions?
  - Drain replacement
  - Seroma/lymphocele aspiration
  - Oral or IV antibiotics
  - Opening of wound
  - Other, specify
- Any other complications (i.e. pneumonia, urinary tract infection, thrombosis, etc.)?
  - No
  - Yes, specify
    - Please enter Clavien-Dindo Grade .....
- Any remarks?

---

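### The ease-or-difficulty part of the surgical resectability objective rests on pre-operative forecasts, and its one comparison item leaves direction to free text or to the paired scores

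*Combined protocol and SAP*

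**What the plan says.** Section 2.3 lists as an exploratory objective "To assess the impact of neoadjuvant therapy on surgical resectability". Section 4.9.1 says the collaborating surgeons will complete "surveys on the subjective difficulty or ease of surgery compared to comparable surgery in patients who have not undergone neoadjuvant therapy". It sets three survey times: enrollment, then "within 1 week of surgical resection and approximately 30 days after surgery is complete". It gives the last survey the task of capturing complications, and it calls the forms in Appendix D samples. Section 7.0 (Statistical Analyses) describes the survey as concerning the difficulty of surgery and cites Appendix D. It plans only a graphical summary of what it acknowledges are subjective data.

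The forms in Appendix D contain the following:

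- **Questionnaire 1** (baseline): basins, number and size of nodes, suspected fixation, and a 1-10 rating of "how difficult do you anticipate the surgery will be if done now".
- **Questionnaire 2** ("To be completed at pre-op visit after completion of neoadjuvant therapy"): the same items and the same 1-10 rating, plus "Do you think the resection is easier or more difficult compared to baseline", answered 'No' or 'Yes, specify'.
- **Questionnaire 3** (headed as 30 days or less from surgery): basins resected, drain removal, "Did the patient have any complications" up to 30 days after the operation with Clavien-Dindo grades, re-operation, re-admission, other interventions and free remarks.

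**The concern.** The stated quantity is how easy or difficult the operation is, relative to comparable operations without neoadjuvant therapy. The forms ask something narrower: how difficult the surgeon expects the operation to be, before and after therapy, in the same patient.

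The study is open-label with one arm, and Section 4.9 places restaging immediately before surgery, so the second forecast comes from a surgeon who knows the treatment and may know the scan result. A fall in the score would show that expectations improved. It would not show that the operation proved easier. A surgeon's rating made soon after operating cannot be reliably reconstructed later if it was not requested at the time.

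Two smaller matters go with this. The comparison item merges two opposite answers into one tick, and the heading of Questionnaire 3 allows a complication form to be closed before its own window has ended.

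**Working it through.** The plan states no figure to reproduce. The check is a reading of every item on the three forms against Sections 2.3, 4.9.1 and 7.0.

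**1. What is rated, and when**

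| Form | Timing on the form | Difficulty rating | Comparison item |
|---|---|---|---|
| Questionnaire 1 | enrollment | 1-10, anticipated | none |
| Questionnaire 2 | pre-op visit | 1-10, anticipated | against own baseline |
| Questionnaire 3 | 30 days or less after surgery | none | none |

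There are two difficulty ratings, both anticipated and both pre-operative. There are no ratings of the difficulty met at operation.

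**2. The comparator.** Section 4.9.1 refers to "subjective difficulty or ease of surgery compared to comparable surgery in patients who have not undergone neoadjuvant therapy". The only comparison item refers to the patient's own state at baseline. One compares a treated patient with untreated patients having similar surgery. The other compares the same patient before and after therapy. The first is asked on no form.

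**3. Coding of the comparison item.** Three answers are possible: easier, no different, more difficult. There are two ticks. 'No' presumably means no different, and 'Yes' covers both other answers. Direction can then come from two places:
- the 'specify' text, which is uncoded;
- the sign of the Questionnaire 2 score minus the Questionnaire 1 score.

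If the two scores are equal and the surgeon ticks Yes, only the free text is left.

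**4. The complication window.** Section 4.9.1 puts the last survey at about 30 days, while Questionnaire 3 is headed 30 days or less. As an illustration, a form completed on day 10 leaves 30 − 10 = 20 days of its own window unobserved. The documents do not say how often forms will be returned early.

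**5. Which contrast to report once an actual score exists.** Let F1 and F2 be the anticipated scores on Questionnaires 1 and 2, and A the score given after surgery. Then

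A − F1 = (F2 − F1) + (A − F2).

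The first bracket compares like with like: the same question, asked before and after therapy. The second is the surgeon's forecasting error at the pre-op visit. A forecast-to-actual difference mixes the two, so A should be shown beside F2 − F1 and not subtracted from F1.

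**The case against.** The strongest case for the plan is that nobody is operated on before therapy in a single-arm trial, so difficulty before treatment can only be forecast. Asking the same 1-10 question twice is a coherent before-and-after measure, and it fits the aim in Section 4.9.1 of learning how first impressions of difficulty change with treatment. The 30-day form is assigned to complications, so its lack of a difficulty item looks deliberate. All of this stands, and it is why the Questionnaire 1 to Questionnaire 2 change should be kept. It does not supply the rating of the operation itself or the comparison with untreated surgery. Calling the forms samples does not supply them either, because Section 7.0 cites Appendix D as the instrument and no other version is given. Free remarks on Questionnaire 3 may mention difficulty but do not ask for it.

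The documents do not support several stronger inferences that a reader might draw:

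- **That the whole resectability objective rests on forecasts.** Questionnaire 3 records observed facts: basins resected, graded complications, re-operation, re-admission and interventions. These serve the purpose in Section 4.9.1 of seeing whether therapy affects surgical outcomes.
- **That direction is lost in Questionnaire 2.** The option asks the surgeon to specify, and the paired scores usually give a sign.
- **That the second survey's timing is contradictory.** Within one week of resection does not say before or after, so a pre-op visit in the preceding week satisfies both places.
- **That fibrosis makes dissection harder, so forecasts will mislead.** Section 4.9 uses fibrosis only to define pathologic response and says nothing about dissection.
- **That complications will be undercounted.** Questionnaire 3 carries its own date and the date of surgery, so an early form can be found and queried. Hospitalizations are captured as serious adverse events. A gap remains for mild events: the recording table in Section 5.0 lists unrelated or unlikely grade 1-2 events for Phase I only.

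**Conclusion.** The point holds for the ease-or-difficulty component. As written, 0 of 3 forms ask how difficult the operation was, and 0 of 3 ask for the comparison with untreated surgery. The single comparison item has no coded direction, and Questionnaire 3 can be completed before its complication window closes.

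The weight is low. The objective is exploratory, the data are to be graphed without a test, and no decision depends on them. The primary analysis, sample size and treatment assignment are unaffected. The missing rating would affect every operated patient. Section 7.0 plans 45 patients but does not say how many will reach surgery, so no count is given here. The conclusion assumes that the Appendix D forms are used as printed; if fuller forms are in use, they should replace those in the appendix.

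**What to change.** 1. **Questionnaire 2:** replace the two ticks on the comparison item with easier / no different / more difficult.
2. **Soon after surgery:** add a 1-10 item asking how difficult the surgery was, and an easier / same / more difficult item that names comparable surgery without neoadjuvant therapy as the reference.
3. **Questionnaire 3:** have the complication items completed on or after day 30, and align the heading with Section 4.9.1.
4. **Section 7.0:** state that the Questionnaire 1 to Questionnaire 2 change summarizes anticipated difficulty, and that the actual score is reported alongside it and not as a forecast-to-actual difference.

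The cost is a form revision and two extra tick-box items for a surgeon who already completes the survey. The ratings made soon after surgery would be filled in earlier than the complication section.

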## Questionnaire 3 ( $\leq$ 30 Days of surgery)

- Surgeon name
- Patient identification
- Date of questionnaire
- Date of surgery
- Which basin(s) did you resect? (can be more than 1)
  - Femoral/Inguinal
  - Iliac/obturator
  - Axilla
  - Cervical
    - Level 1
    - Level 2
    - Level 3
    - Level 4
    - Level 5

- Popliteal
  - Epitrochlear
  - Other, specify
- Date of drain removal
- Did the patient have any complications  $\leq$  30 days postoperatively?
  - No
  - Yes, seroma/lymphocele
    - Please enter Clavien-Dindo Grade .....
  - Yes, surgical site infection
    - Please enter Clavien-Dindo Grade .....
- Was the patient re-operated?
  - No
  - Yes
- Was the patient re-admitted?
  - No
  - Yes
- Did the patient undergo any other interventions?
  - Drain replacement
  - Seroma/lymphocele aspiration
  - Oral or IV antibiotics
  - Opening of wound
  - Other, specify
- Any other complications (i.e. pneumonia, urinary tract infection, thrombosis, etc.)?
  - No
  - Yes, specify
    - Please enter Clavien-Dindo Grade .....
- Any remarks?

---

#### APPENDIX A. Classification of Surgical Complications

Grades	Definition
Grade I:	Any deviation from the normal postoperative course without the need for pharmacological treatment or surgical, endoscopic and radiological interventions. Acceptable therapeutic regimens are: drugs as antiemetics, antipyretics, analgetics, diuretics and electrolytes and physiotherapy. This grade also includes wound infections opened at the bedside.
Grade II:	Requiring pharmacological treatment with drugs other than such allowed for grade I complications. Blood transfusions and total parenteral nutrition are also included.
Grade III:	Requiring surgical, endoscopic or radiological intervention
Grade III-a:	intervention not under general anesthesia
Grade III-b:	intervention under general anesthesia
Grade IV:	Life-threatening complication (including CNS complications) ‡ requiring IC/ICU-management
Grade IV-a:	single organ dysfunction (including dialysis)
Grade IV-b:	multi organ dysfunction
Grade V:	Death of a patient
Suffix 'd':	If the patient suffers from a complication at the time of discharge (see examples in Appendix B, http://Links.Lww.com/SLA/A3 ), the suffix "d" (for 'disability') is added to the respective grade of complication. This label indicates the need for a follow-up to fully evaluate the complication.

‡ brain hemorrhage, ischemic stroke, subarachnoidal bleeding, but excluding transient ischemic attacks (TIA); IC: Intermediate care; ICU: Intensive care unit  
[www.surgicalcomplication.info](http://www.surgicalcomplication.info)

Clavien *et al.* Ann Surg 2009
